
## Intervention

The intervention will be delivered through the Neurorehabilitation and Robotics Clinic at the IU Health Neuroscience Center. All rehabilitation training will be supplied by licensed Physical Therapists with oversight from Research Team. The clinicians involved in the delivery of the intervention will not be involved in outcome assessments. All outcome assessment will be completed by the research team. Participants in both conditions will receive conventional physical therapy (CPT) as usual care. Participants in the Robotic training condition will also receive robot-assisted gait training. The standard group will receive traditional overground walking training. This design will control for attention and social contact, total rehabilitation time, and intensity. Both conditions will be delivered at the same frequency (2x/week), duration (40 to 60 minutes), and time frame over 6-weeks. Progression will occur by increasing the session intensity weekly. Training intensity will be monitored and standardized using the Borg Rating of Perceived Exertion scale and will progress from 'fairly light' (11) to 'somewhat hard' (13). This prescription is consistent and appropriate for individuals with Parkinson's patients with mobility

impairment and low fitness levels. Total training time includes both conventional physical therapy (CPT) and gait training (i.e., 30min of CPT + 30min gait training). Training sessions will not exceed 60 minutes. We will record all training parameters. CPT sessions will involve: 3-5 minute warm-up, stretching, progressive strength training exercises, and balance training. Additional strategies for home exercises, fall prevention, and appropriate assistive devices (i.e., orthotics) will be provided universally.

**Conventional physical therapy (CPT):** A CPT session will involve a 3-5 minute warm-up, stretching, progressive strength training exercises, and balance training (for approximately 30 minutes). Gait training will involve traditional activities that involve overground walking activities, object avoidance, and changing speeds/directions (for approximately 30 minutes).

**G-EO training:** The first 30 minutes will involve a similar CPT session as outlined above. Gait training will focus on using the G-EO System, participants will be secured with the appropriate sized harness and attached to an overhead body-weight support system, with feet secured to pressure sensitive footplates. Gait training sessions will begin with a warm-up in the continuous passive mode (cadence ~40-45 steps/minute). Participants will then be transitioned into the adaptive training mode for practicing repetitive floor walking for up to 30 minutes. During this phase, the force produced by the robot is modulated to support the effort of the patient in producing a typical walking pattern. As the participants improve, intensity of gait training will be increased which will include integration of the stair stepping mode. Total training time will equal 30 minutes.

### **Feasibility and Safety**

Feasibility outcomes will involve process, resources, management, and scientific assessment. Process metrics will include recruitment, retention, and adherence rates assessed by the movement of participants through each stage of the study and training data. Resource metrics will include evaluation of the equipment and facilities through feedback from the therapists. Time to completion relative to proposed target dates will also be reviewed. Management metrics will include data management, documentation of patient progress, record of adverse events, and compliance with approved protocols. Safety will be evaluated through assessment of recorded adverse events.

## **6.0 Reporting of Adverse Events or Unanticipated Problems involving Risk to Participants or Others**

We will monitor participants for any adverse events such as muscle soreness, fatigue, temporary changes in balance/falls, and skin integrity. In the case of an adverse event, the participant's neurologist will be informed of the event. In the case of an adverse event requiring immediate/emergency attention 911 will be called.

## **7.0 Study Withdrawal/Discontinuation**

Participants may withdraw from the study at any time by contacting the program manager ([name]) of Neurorehabilitation and Robotics at [contact]. Additionally, participants may communicate their desire to withdraw from the study to any of the study's investigator: [name] [contact]).

## **8.0 Statistical Considerations**

Data will be analyzed using IBM SPSS Version 25.0 (IMB Corps., Armonk, NY). Descriptive statistics will characterize the sample on demographic, clinical, safety, and feasibility metrics. We will compare safety and feasibility between groups using chi-square and *t*-tests for independent samples (*Specific Aim 1*). The efficacy of the intervention on study variables (*Specific Aim 2*) will be examined using a 2 (Group) by 2 (Time), mixed factor ANOVA. A completers analysis will be conducted (i.e.,  $\geq 75\%$  of sessions completed). Effect sizes associated with F-statistics will be expressed as eta-squared ( $\eta^2$ ), and effect sizes based on mean differences will be expressed as Cohen's *d*.

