## **2.0 Rationale and Specific Aims**

The logistic advantages and advanced training capabilities of the G-EO System, as well as the benefits reported in other populations, support this strategy as an effective rehabilitation tool for restoring and maintaining function in Parkinson's disease. This approach represents an opportunity for improving current clinical practices for patients with Parkinson's disease. If successful, this project will provide initial evidence for increasing patient access to the G-EO System, and this could be accomplished through "regional technology centers" using a rural health-delivery approach.

The purpose of this study is to investigate the implementation of a novel gait rehabilitation stimulus (G-EO System) that could advance current clinical practices. The goal is to establish the

safety and feasibility of gait training using the G-EO System as well as investigating the impact on mobility, function, quality of life, and participatory outcomes.

**Research Design:** We propose a single-blinded, randomized trial of electromechanically-assisted gait training using the G-EO System in patients with Parkinson's disease with gait disability.

*Specific Aim 1* will establish the safety and feasibility of gait training using the G-EO System.

*Specific Aim 2* will determine the efficacy of gait training using the G-EO System for improving mobility, function, quality of life, and participatory outcomes.

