### **4.0 Enrollment/Randomization**

A convenience sample of 30 persons with Parkinson's Disease will be enrolled for this clinical trial. Recruitment will occur through neurologists at the IU Health Neuroscience Center. Each participant will be given time to read the consent form or have it read to them and to ask questions (see Informed Consent Draft). Consent will be obtained before initial assessments and treatment randomization. The consent process will take place at the Indiana Center for Advanced Neurorehabilitation (ICAN) in the Neurorehabilitation and Robotics IU Health Neuroscience Center, [name] [contact].

If found eligible for the study and agree to consent to participate, subjects will be randomized to either conventional physical therapy (CPT) group or CPT with G-EO training using a random numbers generator and concealed allocation.

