### **Assessments**

The study outcomes will be collected by treatment-blinded researchers. All participants on Day 1 who consent to be in the study will complete the following mobility outcomes:

1. Spatial and temporal gait kinematics will be assessed using a PKMAS Zeno Walkway (Protokinetics). Participants will be asked to walk over a 14-foot pressure mat that will capture their gait kinematics and speed. Comfortable and fast walking speed will be assessed. (10 minutes)
2. A 6-minute walk (6MWT) tests to determine walking endurance. Subjects will be asked to walk for 6 minutes along a 30m track. Subjects may stop and rest as often as needed. Subject walking speed will be collected during the test to evaluate rate of functional fatigue. (10 minutes)
3. Balance assessment using the Mini BESTest. Subjects will be asked to complete 14 different tasks ranging from static standing to dynamic walking. All subjects will be guarded closely for safety to prevent falling. (15 minutes)
4. The level of lower extremity functional strength combined with balance will be assessed by the five times sit to stand test. (5 minutes)
5. Performance translation of balance improvement will be measured using the self-report Activities Balance Confidence Scale. (10 minutes)
6. Their level of health-related quality of life assessed by the Parkinson's disease Questionnaire-39. (15 minutes)
7. Obstacle management while walking. Patients will be asked to walk over a flat firm surface for 14 meters. The pathway will include a box that is one foot by one foot that each person. (6 passes; 10 minute break; 6 passes; 10 minute break; 6 passes; 10 minute break) total of 40 minutes
8. Performance translation to real life activities will be measured by accelerometers. Each participant will wear an accelerometer at home to measure activity levels. (completed at home)
- After completing all of therapy, the research team will complete a short interview with the participant. The interview will focus on their experiences during therapy regardless of which group they participated in. We will also ask them to consider how valuable they think the experience was for their health. This interview will take about 15 minutes.

Participants will complete outcome assessments prior to the start of the study, at the end, and one month following completion.

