### **Schedule**

Following completion of day 1 assessments, all subjects will be scheduled for the intervention phase of the study. Regardless of group allocation, each participant will receive 12 total visits scheduled ideally two times a week for 6 weeks. Following completion of the 12 visits each subject will complete all outcome assessments. (See Table 1) If a subject cancels a treatment session, it will be rescheduled to ensure that all subjects complete the total of 12 treatment sessions prior to final testing. If a subject misses three consecutive treatment sessions, they will be dropped from the study due to inconsistency in treatment carryover. Cancellations and changes

in patient scheduling is a part of true clinical experience and represents normal clinical patient management. Therefore, the emphasis is on total number of treatments (12) and not on total number of weeks.

Pre-Intervention Phase		Intervention Phase	Post Intervention	Follow Up
Day 1	Day 2 Measurement	6 weeks intervention period	Post Assessment	 Month Follow Up

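### Outcomes are measured at three times, but the only efficacy analysis has two unnamed time levels, so one wave has no pre-specified analysis

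*Combined protocol and SAP*

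**What the plan says.** The Assessments part of Section 5.0 sets three measurement times: "Participants will complete outcome assessments prior to the start of the study, at the end, and one month following completion". The schedule table in the same section agrees. Its column headed "Month Follow Up" repeats the same eight-item battery that appears in the pre-intervention and post-intervention columns.

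Section 8.0 is the whole statistical plan. Its one efficacy analysis, for Specific Aim 2, "will be examined using a 2 (Group) by 2 (Time), mixed factor ANOVA". The two time points are not identified. Section 8.0 also contains:

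- descriptive summaries, whose scope is given as "Descriptive statistics will characterize the sample on demographic, clinical, safety, and feasibility metrics";
- chi-square and t-tests for safety and feasibility (Aim 1);
- a restriction by attendance: "A completers analysis will be conducted", defined as at least 75% of sessions;
- a choice of effect-size measures.

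None of these refers to the one-month visit. Section 2.0 says that Aim 2 "will determine the efficacy of gait training using the G-EO System for improving mobility, function, quality of life, and participatory outcomes". It names no time point and does not mention retention of effect.

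**The concern.** A two-level time factor cannot hold three waves, so one wave falls outside the stated model. Because the levels are unnamed, the analyst must choose a pair of visits before the test can be run. The plan names no primary outcome or primary time point that would settle the choice, and it recurs for each of the eight measures.

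Two things are at stake. First, if the choice is made after the data are seen, each outcome has two chances to show a group difference. Second, a two-level interaction tests a single between-group difference in change, so it cannot separate an effect present at the end of training from one still present a month later. Participants would go through a third assessment (105 timed minutes by the protocol's own durations, plus home accelerometry) with no stated analytic use for one of the three sets of results.

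**Working it through.** **Inputs from the documents**

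- Sample size N = 30 (Section 4.0: "A convenience sample of 30 persons"). No alpha, power, effect size, SD or dropout rate is given, so this figure cannot be reproduced or challenged.
- Groups G = 2 (Section 4.0: "subjects will be randomized to either conventional physical therapy (CPT) group or CPT with G-EO training").
- Scheduled assessments: 3 (Section 5.0, text and table).
- Time levels in the model: 2 (Section 8.0).
- Durations of the timed assessments (Section 5.0).

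**Assumed:** two-sided alpha of 0.05, complete data unless stated, and the missingness rates in step 5.

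**1. Waves against time levels.** Scheduled per outcome: 30 × 3 = 90 participant-assessments. Used by a two-level model: 30 × 2 = 60. Left over: 90 − 60 = 30, or one third.

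**2. Burden of one wave.** 10 + 10 + 15 + 5 + 10 + 15 + 40 = 105 minutes per participant, plus accelerometry at home.

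**3. What the stated test can address.** The group-by-time interaction has (G − 1)(T − 1) and (N − G)(T − 1) degrees of freedom.

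| Time levels | Degrees of freedom | Critical F at 0.05 |
|---|---|---|
| 2 (as planned) | 1 and 28 | 4.20 |
| 3 (matching the schedule) | 2 and 56 | 3.16 (4.20 with the lower-bound sphericity correction) |

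The planned test has one degree of freedom for one contrast. Two questions, end of treatment and one month, need two contrasts.

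**4. Effect of leaving the pair open.** If both pairs were tested at 0.05 and either could be reported, the chance of at least one false positive per outcome would be 1 − 0.95² = 0.0975 with independent tests. The tests share a baseline and the same participants, so they are correlated. Under a bivariate normal approximation the figure is about 0.091 at a test correlation of 0.5 and 0.078 at 0.8. These correlations are assumptions.

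**5. The simplest repair: a third level in the same ANOVA.** The plan does not propose this. It is checked here only because it is the obvious patch. Repeated-measures ANOVA in SPSS keeps complete cases only. With missingness m at each of the two later visits, the loss is m if the same people miss both (fully nested) and 1 − (1 − m)² if the visits are missed independently.

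| Assumed m per visit | Nested loss | Independent loss |
|---|---|---|
| 10% | 10% (3 of 30) | 1 − 0.90² = 19% (5.7 of 30) |
| 15% | 15% (4.5 of 30) | 1 − 0.85² = 28% (8.3 of 30) |

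Section 5.0 drops anyone who misses three consecutive sessions. Such a person would probably miss both later assessments, which points towards the nested end of each range.

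**The case against.** The strongest reply is that baseline to end of treatment is the natural pair, that it answers Aim 2 as worded, and that leaving out the follow-up does not bias that comparison. This is a convenience sample of 30 with safety and feasibility as its first aim, so an unanalysed secondary wave is a modest matter. Much of this stands, and it limits the point in four ways.

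- A reader might infer that the one-month visit is definitely the omitted one. The documents do not say so. If the pair were baseline and one month, the end-of-treatment data would be left out instead.
- A reader might infer that the trial can draw no conclusion about persistence. That is too strong. No aim names persistence, the data will exist, and they can be examined post hoc. What is missing is a pre-specified analysis.
- A reader might take 19% or 28% as the loss under this plan. Those figures belong to a three-level ANOVA that the plan does not contain, and they require independent missingness.
- The inflation from two chances is real but smaller than the independence figure of 0.0975.

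The reply does not remove the mismatch itself. A reader can guess the intended pair but cannot confirm it from the text, and under either reading one collected wave has no stated analysis.

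**Conclusion.** The concern holds in limited form. Three waves are scheduled, the sole efficacy model takes two unnamed ones, and nothing else in Section 8.0 covers the third. The size that follows from the documents is one wave in three: up to 30 of 90 participant-assessments per outcome, if all 30 participants complete every visit. That the one-month visit is the omitted wave is likely but inferred. The choice of second time point is open for each outcome. At an assumed alpha of 0.05, using that freedom would raise the per-outcome false-positive rate to roughly 0.08 to 0.10, depending on the assumed correlation. A retained effect could be reported only as a post hoc finding.

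**What to change.** Make the change before outcome data are examined. Later, it no longer protects against a selective choice of time point.

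**Preferred**

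- State that the efficacy result for each outcome is the between-group difference at the end-of-treatment assessment, and that the one-month difference is secondary. Report each with a 95% confidence interval.
- Estimate both from one linear mixed model per outcome (SPSS MIXED). Use group, visit (post, one month), group-by-visit and the baseline value, with unstructured covariance within participant. With two post-baseline visits this covariance has three parameters (two variances and one covariance), which is workable at N = 30.
- Include all randomised participants with at least one post-baseline value. Someone seen at only one later visit then still contributes. Someone with neither visit does not, and the number of such participants should be reported by group.
- Keep the completers analysis (at least 75% of sessions) as a separate, labelled analysis, so that the two populations are not confused.

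**Minimum**

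- Keep the ANOVA, name its two time points, and state how the third wave will be analysed, or label that wave exploratory and say what will be reported. If a third time level is added instead, specify a sphericity correction and acknowledge the complete-case loss.

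**Cost:** SAP wording and slightly more analysis work. No new data, visits or software are needed.

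### The efficacy ANOVA is in effect a change-score test; ANCOVA on baseline values already collected is usually more precise and adjusts for chance imbalance in that baseline

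*Combined protocol and SAP*

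**What the plan says.** Section 8.0 (Statistical Considerations) states that efficacy on the Aim 2 variables will be tested with a "2 (Group) by 2 (Time), mixed factor ANOVA". Baseline enters only as one level of the Time factor. No covariate is named there or elsewhere, and the section does not say which of the three ANOVA effects is the treatment test. It adds: "A completers analysis will be conducted", with completion defined as at least 75% of sessions.

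Section 4.0 (Enrollment/Randomization) gives the size as "A convenience sample of 30 persons" and allocates participants to two arms "using a random numbers generator and concealed allocation". It states no ratio, blocking or stratification.

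The baseline data will exist. Section 5.0, Assessments, says: "Participants will complete outcome assessments prior to the start of the study, at the end, and one month following completion". The schedule table lists the same eight measures at all three points.

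The sections differ on when baseline is taken. The text under Assessments and under Schedule puts it on Day 1. The schedule table puts random assignment on Day 1 and outcome measurement on Day 2.

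**The concern.** A change score subtracts the whole baseline value, which is right only if the regression of the final value on baseline has slope 1. When the slope is smaller, the subtraction over-corrects: an arm that happens to start higher tends to show less gain, and an arm that starts lower tends to show more, with no treatment effect at all. Over repeated randomisations these errors cancel, but in any one trial they do not. With 30 people and no stratification stated, a noticeable gap in some outcome's baseline would be unremarkable. The over-correction also adds noise, so intervals are wider than they need to be in a trial with no power calculation behind it.

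The test is also not identified. Of the three effects that the ANOVA prints, only the interaction compares the arms on change. The Time effect pools both arms, each of which receives active therapy. The Group effect averages the pre-treatment visit with the later one and so halves any true difference.

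**Working it through.** **Inputs.** From the documents: 30 participants, two arms, two Time levels, baseline measured for every outcome. Not given, so assumed: 15 per arm, equal SD at both visits (scaled to 1), two-sided 5% level, approximately normal outcomes, and a pre-post correlation r between 0.3 and 0.95. The figure of 30 cannot be reproduced, because no alpha, power, effect size or SD is stated.

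**Step 1: what the interaction tests.** On one simulated 15-versus-15 data set, the Group x Time F was 2.12679 and the squared two-sample t on change scores was also 2.12679. They are algebraically the same test.

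**Step 2: precision.**
- Change-score variance per person: 2(1 − r).
- ANCOVA residual variance: 1 − r².
- Large-sample ratio: (1 − r²) / [2(1 − r)] = (1 + r)/2.
- Cost of estimating the slope at N = 30: multiply by (N − 3)/(N − 4) = 27/26.

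| r | (1 + r)/2 | × 27/26 |
|---|---|---|
| 0.3 | 0.65 | 0.675 |
| 0.5 | 0.75 | 0.779 |
| 0.7 | 0.85 | 0.883 |
| 0.8 | 0.90 | 0.935 |
| 0.9 | 0.95 | 0.987 |
| 0.95 | 0.975 | 1.012 |

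Simulations of 15 per arm agree: about 0.68, 0.78, 0.88, 0.93, 0.99 and 1.01 to 1.02.

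Break-even is where (1 + r)/2 × 27/26 = 1, so r = 52/27 − 1 = 0.926. If only 24 people are analysed it is 2 × 20/21 − 1 = 0.905. Above break-even the loss is small: about 1 to 2% of variance at r = 0.95.

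In practical terms, at r = 0.7 the interval narrows by 1 − √0.883 = 6%, and the gain is like having 30/0.883 = 34 participants instead of 30. For an assumed true effect of 0.8 SD, simulated power for change score versus ANCOVA is 56% versus 67% at r = 0.5, 78% versus 83% at r = 0.7, and 92% versus 93% at r = 0.8.

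**Step 3: chance imbalance.**
- SE of the baseline difference: √(2/15) = 0.365 SD.
- P(|gap| > 0.5 SD): 0.5/0.365 = 1.37, two-sided probability 0.171.
- Conditional bias of the change-score estimate: (1 − r) × gap. For a gap of exactly 0.5 SD this is 0.25, 0.15 and 0.05 SD at r = 0.5, 0.7 and 0.9.
- For scale, the SE of the change-score comparison at r = 0.7 is √(0.6 × 2/15) = 0.28 SD, so 0.15 SD is about half a standard error.

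Among simulated null trials with a gap above 0.5 SD, mean change-score bias was about 0.33, 0.20 and 0.13 SD at r = 0.5, 0.7 and 0.8, and the false-positive rate was about 12%, 9% and 8%. ANCOVA had bias below 0.01 SD and a rate near 5%. Over all simulated trials, with or without a gap, both methods held about 5%.

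**Step 4: the equal-SD condition.** Let k be the ratio of post SD to baseline SD. Change variance is 1 + k² − 2rk and ANCOVA variance is k²(1 − r²). The difference is 1 − 2rk + r²k² = (1 − rk)². It is never negative, but it is zero when k = 1/r (k = 1.43 at r = 0.7; 1.11 at r = 0.9). The ratios in Step 2 therefore hold only for k = 1; other values can enlarge or shrink the gain.

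**The case against.** The strongest reply is that nothing here is broken. Allocation is random and concealed, so the change-score comparison is unbiased over randomisations and keeps its 5% error rate. That stands. A reader might infer from the conditional bias that the planned test is invalid or yields too many false positives overall; the documents and the calculation do not support that.

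The benefit also depends on a correlation that the documents do not give. If r is 0.8 or more the gain is small, and above about 0.93 it becomes a slight loss. This stands too, and it is why the size is given as a range. The asymmetry still favours ANCOVA: over r = 0.3 to 0.95, the most it loses is about 1 to 2% of variance, and the most it saves is about a third.

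A gap above 0.5 SD is a minority event, at 17% per outcome, and its effect at r = 0.7 is about half a standard error. It is real, but it would not dominate the result.

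Finally, one might infer that a shared improvement over time will be credited to the G-EO System. Section 8.0 does not say that the Time or Group main effect will be read as efficacy, and the interaction is the conventional test in this design. What stands is only that the plan should name the effect it will use.

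**Conclusion.** The concern holds as one of efficiency and of bias conditional on an observed imbalance. The planned analysis is usable but usually inferior to one that needs no further data. Under equal SDs and 15 per arm, ANCOVA has about 78%, 88% and 99% of the change-score variance at r = 0.5, 0.7 and 0.9. It breaks even near r = 0.93 and is slightly worse beyond that.

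Two stronger claims should not be made. ANCOVA is not more precise at every correlation. Nor does it remove baseline imbalance in general: it adjusts for imbalance in the measured baseline of the outcome being analysed, not for disease stage, medication or other factors.

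The algebra is certain. The size of the benefit is not, because the correlation, the SD ratio, the allocation split and the number finally analysed are all absent from the documents. This is a change that the plan should make, though the trial does not fail without it.

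**What to change.** In Section 8.0, replace the ANOVA sentence with wording such as: each Aim 2 outcome will be analysed by ANCOVA, regressing the end-of-treatment value on randomised group and the participant's baseline value of the same outcome; the group coefficient with its 95% CI is the efficacy result. Add that the one-month value will be analysed in the same way as a separate, secondary comparison. This names the visit and leaves no doubt about which effect counts.

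Reconcile the Assessments and Schedule text with the schedule table, so that the baseline covariate is clearly measured before allocation is known. This matters most for the self-reported balance-confidence and quality-of-life scales, where a participant who knows the assignment could answer differently.

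The cost is a few sentences and one degree of freedom per model (27 residual degrees of freedom instead of 28 with 30 analysed). No visit, instrument or participant is added. The change does not repair the restriction to completers, which needs its own correction.

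### Completers are the only efficacy population the plan names, and a separate drop rule also lets attendance after randomisation decide who enters the Aim 2 comparison

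*Combined protocol and SAP*

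**What the plan says.** Section 8.0 assigns Specific Aim 2 to a group-by-time "mixed factor ANOVA" with two groups and two times. It does not say which randomised participants enter that model. The next sentence reads "A completers analysis will be conducted", and a parenthesis sets the threshold at 75% or more "of sessions completed". No intention-to-treat, full-analysis or per-protocol set is defined anywhere, and no method for missing outcomes is given.

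The Schedule in Section 5.0 bears on the same question in three places:

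- Planned dose of sessions: "each participant will receive 12 total visits scheduled ideally two times a week for 6 weeks".
- Cancelled sessions: a cancelled session is made up, in that "it will be rescheduled to ensure that all subjects complete the total of 12 treatment sessions prior to final testing".
- Missed sessions: "If a subject misses three consecutive treatment sessions, they will be dropped from the study due to inconsistency in treatment carryover".

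Neither the Schedule nor Section 7.0 (withdrawal) describes any assessment after a participant is dropped or withdraws. The Assessments section places outcome measurement before the study, at its end and one month later. Feasibility and Safety lists retention and adherence as outcomes, and Section 8.0 compares feasibility between the arms.

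**The concern.** Randomisation protects the comparison only if the people compared are those who were randomised. Attendance is observed after allocation and may depend on it. Only the G-EO arm trains in a harness, on body-weight support, with the feet fixed to footplates. Section 6.0 anticipates soreness, fatigue, balance changes or falls, and skin problems. The plan itself treats retention and adherence as quantities to be compared between arms, so it accepts that they may differ, and yet attendance also filters the efficacy data.

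What is at stake is the meaning of the Aim 2 estimate. If, for example, people who respond poorly to the robot stop attending while those in conventional therapy stop for unrelated reasons, poor feasibility under Aim 1 would raise apparent efficacy under Aim 2. If the better responders stop, the distortion runs the other way. With two-level Time, a participant who has no post-treatment measurement cannot contribute to the ANOVA at all. Outcomes that were never collected cannot be recovered at analysis.

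**Working it through.** The plan gives no power calculation, effect size, SD, alpha or dropout rate, and describes its sample this way: "A convenience sample of 30 persons with Parkinson's Disease will be enrolled for this clinical trial". There is therefore no stated figure to reproduce.

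**Step 1. Who enters the comparison.** The completer threshold is 0.75 × 12 = 9 sessions. Two readings of Section 8.0 are possible.

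- *Completers are the main analysis.* Anyone with fewer than 9 sessions is excluded.
- *Completers are an addition to an unrestricted ANOVA.* The ANOVA still needs both a pre and a post value. Someone dropped after three consecutive missed sessions has no post assessment described, and so does not enter.

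Both readings select on attendance. The passages also fail to fit together: the Schedule ties final testing to all 12 sessions, while Section 8.0 counts 9 as complete. Whether and when someone with 9 to 11 sessions is tested is not stated.

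**Step 2. Size of a possible bias (illustration only).** Assumed inputs: 15 per arm (30 ÷ 2; the allocation ratio is not stated), a change score y with SD 1, no true effect, and a two-sided t-test at 0.05. That test is equivalent to the group-by-time test of a two-by-two mixed ANOVA. In the robot arm each participant has an attendance score ρy + √(1 − ρ²)·e, with e standard normal noise, and the k lowest are excluded. The control arm has no exclusions. There were 40,000 simulated trials per scenario.

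| k of 15 excluded, robot arm | Bias, ρ = 0.3 | Bias, ρ = 0.7 | Type I error, ρ = 0.3 to 0.7 |
|---|---|---|---|
| 2 | 0.07 SD | 0.16 SD | 0.055 to 0.078 |
| 3 | 0.10 SD | 0.23 SD | 0.057 to 0.095 |
| 4 | 0.13 SD | 0.30 SD | 0.064 to 0.122 |
| 5 | 0.16 SD | 0.36 SD | 0.065 to 0.147 |

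A check: the bias should equal ρ times the mean of the 15 − k largest of 15 standard normal values. For k = 3 that mean is about 0.33, giving 0.3 × 0.33 = 0.10 and 0.7 × 0.33 = 0.23, as in the table.

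Three boundary cases:

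- ρ = 0: bias 0.00 SD and type I error 0.05, whatever k.
- Three excluded in each arm, with the control exclusions unrelated to outcome: bias 0.10 to 0.23 SD, type I error 0.058 to 0.096. Equal counts do not remove the bias when the reasons differ.
- No exclusions and complete data: bias 0.00 SD, type I error 0.05.

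By symmetry, excluding the best responders instead of the worst reverses the sign.

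**Step 3. Scale against sampling error.** With k excluded from one arm, the standard error of the standardised difference is about √(1/(15 − k) + 1/15). For k = 2 it is √(1/13 + 1/15) = 0.38, so the smallest bias is 0.07/0.38 = 0.18 of a standard error. For k = 5 it is √(1/10 + 1/15) = 0.41, so the largest is 0.36/0.41 = 0.88.

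**Step 4. Precision.** The difference detectable with 80% power (two-sided 0.05, noncentral t) is d = 1.06 at 15 per arm, 1.20 if 12 per arm remain and 1.33 if 10 per arm remain.

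**The case against.** The strongest objection concerns the text. Section 8.0 first states the ANOVA with no population restriction and then adds the completers analysis in a separate sentence, with an indefinite article and without calling it primary or sole. A reader might infer that efficacy will be analysed in completers only and that an all-randomised analysis has been ruled out. The documents do not support that: they leave the main population undefined. This part of the objection stands. It does not remove the problem, because the drop rule in the Schedule limits an unrestricted ANOVA as well.

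The second objection is that exclusions may be few. Cancelled sessions are rescheduled, the emphasis is on reaching 12 sessions however long that takes, and the threshold is only 9. The arms also share visit frequency, session length and roughly 30 minutes of conventional therapy, so only the gait-training half differs. This also stands. No dropout rate is given, so the numbers excluded in the illustration are assumptions and not forecasts.

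Third, a reader might infer that the bias is certain and favours the robot. It is neither. It needs attendance to relate to outcome differently by arm, and its sign depends on who stops.

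Finally, this is a convenience sample of 30 with safety and feasibility as its first aim, and every bias in the table is smaller than one standard error. That limits how much weight the size can carry. Specific Aim 2 is nevertheless an efficacy aim in a randomised trial, and it needs a defined population.

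**Conclusion.** The concern holds in this form: completers are the only efficacy population named, no all-randomised analysis is stated, and the drop rule lets attendance after randomisation decide who enters the pre/post comparison under either reading of Section 8.0. That much follows from the documents alone.

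The bias is conditional. It is zero if attendance is unrelated to outcome, can take either sign, and may be small if rescheduling works. Under the assumed 15 per arm, 2 to 5 robot-arm exclusions and a correlation of 0.3 to 0.7, it is about 0.07 to 0.36 SD, with type I error of about 0.055 to 0.15 against a nominal 0.05. The case for changing the plan rests on the missing all-randomised analysis together with the drop rule, not on any one of these figures. The change should be made before outcomes are lost.

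**What to change.** **Section 8.0.** State that the primary efficacy analysis includes every randomised participant in the arm assigned, whatever number of sessions was completed. Use a mixed model on all available outcome data, with baseline included as a measurement, and state its missing-at-random assumption. Label the completers analysis (at least 75% of sessions) as supportive only. Report the number of non-completers and their reasons by arm.

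**Section 5.0, Assessments and Schedule.** Seek the post-treatment and one-month assessments from every randomised participant who agrees, whether or not they continue sessions. Without this the new wording in Section 8.0 falls short: a mixed model cannot restore outcomes never collected, and relies on the missing-at-random assumption for those people.

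**Reconcile the passages.** The requirement for 12 sessions before final testing, the rule that drops participants from the study, and the 75% threshold must be made consistent, including whether and when someone with 9 to 11 sessions is assessed. How treatment attendance itself is managed is for the investigators.

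**Cost.** This is more than SAP wording, because it changes a protocol procedure. The assessments are already scheduled, so the added burden is a few visits by people who have stopped sessions. The estimate may be slightly diluted by poor attenders.
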